1. PROTOCOL SYNOPSIS FOR STUDY BTZ116849

Rationale

This study will be conducted to determine if altered renal function affects the plasma pharmacokinetics of gepotidacin, which will inform if dosing recommendations based upon renal impairment are required. The proposed single IV infusion dose of gepotidacin 750 mg administered over 2 hours will provide an approximate 2.5-fold margin for area under the plasma concentration-time curve (AUC) and maximum observed concentration (C_{max}) based on the highest single IV dose of gepotidacin (1800 mg) evaluated in adult healthy subjects.

Objectives/Endpoints

Objectives	Endpoints
Primary	

 To compare the pharmacokinetics of gepotidacin administered as a 750-mg IV dose in normal healthy subjects compared with subjects with mild, moderate, and severe renal impairment, and with subjects with end-stage renal disease (ESRD) 	
 Plasma primary pharmacokinetic (PK) endpoints include AUC(0-∞) and C_{max} of gepotidacin, as data permit Urine primary PK end points include Ae total, fe%, and CL_r of gepotidacin, as data permit Dialysate primary PK end points include AUC(t0-t1), CL_D, and Frem%(0-4), of gepotidacin, as data permit
Secondary	

 To assess the safety and tolerability of gepotidacin administered as a 750-mg IV dose in normal healthy subjects compared with subjects with mild, moderate, severe renal impairment, and with subjects with ESRD 	
 12-lead safety electrocardiogram readings, change from baseline in vital sign measurements (blood pressure and heart rate), monitoring of adverse events, toxicity grading of clinical laboratory test results, and physical examinations

 To evaluate the secondary PK parameters of gepotidacin administered as a 750-mg IV dose in normal healthy subjects compared with subjects with mild, moderate, and severe renal impairment, and with subjects with ESRD 	
 Plasma PK endpoints include AUC(0-t), CL, λ_z, t_{1/2}, T_{max}, V_{ss}, and V_z, as data permit Urine PK endpoint includes Ae(t1-t2), as data permit Dialysate PK endpoints include Arem(0-1), Arem(1-2), Arem(2-3), Arem(3-4), and Arem(0-4), as data permit
Exploratory	

 To evaluate the saliva pharmacokinetics of gepotidacin (subjects in Part 1 only) 	
 Primary PK endpoints include AUC(0-∞) and C_{max} of gepotidacin, as data permit Secondary PK endpoints include AUC(0-t), CL, λ_z, t_{1/2}, T_{max}, V_{ss}, and V_z, as data permit

ESRD = end-stage renal disease; PK = pharmacokinetic

Overall Design

This is a Phase I, nonrandomized, open-label, parallel-group, multi-center, multi-part study that will evaluate the pharmacokinetics, safety, and tolerability of a single IV dose of gepotidacin 750 mg over 2 hours in subjects with normal renal function, subjects with mild, moderate, and severe renal impairment, and subjects with end-stage renal disease (ESRD; on dialysis and not on dialysis).

Subjects will be enrolled into groups based on the classification as defined in the United States Food and Drug Administration draft guidance for industry, "Pharmacokinetics in Patients with Impaired Renal Function – Study Design, Data Analysis, and Impact on

Dosing and Labeling” [DHHS, 2010]. Subjects with normal renal function and subjects with renal impairment will be classified based on the estimated glomerular filtration rate (eGFR; based on the Modification of Diet in Renal Disease Study). Subjects with normal renal function will also be classified based on estimated creatinine clearance (Clcr).

This will be a multi-part study, in which pharmacokinetic (PK) requirements must be met (observed mean values: AUC <48 $\mu\text{g}\cdot\text{hr}/\text{mL}$ and C_{max} <14 $\mu\text{g}/\text{mL}$); and safety and tolerability will be reviewed before enrolling subjects into the next part of the study. In Part 1, subjects with normal renal function; subjects with moderate renal impairment; and subjects with severe renal impairment and subjects with ESRD not on hemodialysis will be enrolled. In Part 2 (optional), subjects with normal renal function, subjects with mild renal impairment, and subjects with ESRD on hemodialysis will be enrolled based on the PK, safety, tolerability, and data results of Part 1.

Subjects with renal impairment will be matched to subjects with normal renal function in terms of gender distribution, age (approximately ± 10 years), and body mass index (approximately $\pm 20\%$).

Treatment Arms and Duration

Subjects will be screened within 30 days prior to entry to the clinic and will be enrolled as follows:

Part 1:

- Group A: subjects with normal renal function ($\text{eGFR} \geq 90 \text{ mL}/\text{min}/1.73\text{m}^2$)
- Group B: subjects with moderate renal impairment (eGFR 30 to 59 $\text{mL}/\text{min}/1.73\text{m}^2$)
- Group C: subjects with severe renal impairment and subjects with ESRD not on hemodialysis ($\text{eGFR} < 30 \text{ mL}/\text{min}/1.73\text{m}^2$)

If PK, safety, and tolerability requirements are not met in Part 1, and based on the emerging data, and/or data that are not expected to exceed the requirements in the subjects with ESRD on hemodialysis or may require dose adjustment, subjects for Part 2 will be enrolled. In addition, based on emerging data from Part 1, Group E may not be enrolled in Part 2 (optional).

Part 2 (Optional):

- Group D: subjects with normal renal function ($\text{eGFR} \geq 90 \text{ mL}/\text{min}/1.73\text{m}^2$)*
- Group E: subjects with mild renal impairment (eGFR 60 to 89 $\text{mL}/\text{min}/1.73\text{m}^2$)
- Group F: subjects with ESRD on hemodialysis

* If there are a sufficient number of subjects with normal renal function enrolled in Part 1 (Group A) that match subjects with renal impairment in other groups, a determination will be made regarding the enrollment of matching subjects with normal renal function in Part 2 (Group D).

Subjects in Groups A, B, C, D, and E will enter the clinic at Check-in (Day - 1, Period 1) before study drug administration (Day 1, Period 1). In Parts 1 and 2, on Day 1 (Period 1),

subjects in Group A, B, C, D, and E will receive a single dose of study drug as follows: gepotidacin 750 mg administered as a 2-hour IV infusion. All subjects will be discharged from the clinic on Day 3 after all scheduled PK and safety assessments have been completed, and will return to the clinic for a Follow-up Visit approximately 10 days (± 5 days) after dose administration. The duration of the study (from Screening to the Follow-up Visit) will be approximately 44 days.

In Part 2 (optional) of the study, subjects in Group F will participate in 2 treatment periods, with dosing in these periods separated by a washout period of at least 7 days. Subjects in Group F will enter the clinic at Check-in (Day -1, Period 1 and Day 7, Period 2) before each study drug administration (Day 1, Period 1 and Day 8, Period 2). On Day 1 (Period 1) and Day 8 (Period 2), subjects in Group F will receive a single dose of study drug as follows: gepotidacin 750 mg administered as a 2-hour IV infusion starting approximately 2 hours before the initiation of the last hemodialysis session of the week (Period 1) and gepotidacin 750 mg administered as a 2-hour IV infusion starting within 2 hours after completion of the last hemodialysis session of the week (Period 2). Subjects in Group F will be discharged from the clinic on Day 10, Period 2 after all scheduled PK and safety assessments have been completed, and will return to the clinic for a Follow-up Visit approximately 10 days (± 5 days) after the last dose administration in Period 2. The duration of the study (from Screening to the Follow-up Visit) will be approximately 50 days.

Type and Number of Subjects

In Part 1, up to 16 subjects with normal renal function will be matched to approximately 8 subjects with moderate renal impairment, and approximately 8 subjects with severe renal impairment and/or subjects with ESRD not on hemodialysis for a total of approximately 32 subjects. In Part 2 (optional), approximately 4 to 8 subjects with normal renal function (if enrolled), approximately 4 to 8 subjects with mild renal impairment, and approximately 4 to 8 subjects with ESRD on hemodialysis will be enrolled for a total of approximately 12 to 24 subjects.

If there are a sufficient number of subjects with normal renal function enrolled in Part 1 (Group A) that match subjects with renal impairment in other groups, a determination will be made regarding enrollment of matching subjects with normal renal function in Part 2 (Group D). In addition, if subjects prematurely discontinue the study, additional replacement subjects may be enrolled at the discretion of the Sponsor in consultation with the investigator.

Analysis

Plasma and saliva concentrations of gepotidacin will be analyzed (as data permit) by noncompartmental PK analysis to determine the following PK metrics: AUC from hour 0 to the last measurable plasma concentration (AUC(0-t)), AUC extrapolated to infinity (AUC(0- ∞)), C_{max}, time to maximum concentration (T_{max}), apparent terminal phase half-life (t_{1/2}), systemic clearance (CL), volume of distribution at steady-state of parent drug (V_{ss}; plasma only), and volume of distribution of the terminal phase (V_z).

Urine concentrations of gepotidacin will be analyzed (as data permit) by noncompartmental PK analysis to determine the following PK metrics: total unchanged drug (A_e total), amount of drug excreted in urine (A_e (t1-t2)), percentage of the given dose excreted in urine (fe%), and renal clearance (Cl_r).

Plasma, urine, and saliva (subjects in Part 1 only) concentrations of gepotidacin and the associated PK parameters will be listed, and summary statistics (n, mean, median, standard deviation, minimum, maximum, and coefficient of variation) will be presented by day and treatment. Mean and individual plasma concentration versus time profiles will be presented graphically on linear and semilogarithmic scales.

Dialysate concentration of gepotidacin will be analyzed for all subjects with ESRD on dialysis (Group F subjects in Part 2 [optional]) to determine the following PK metrics: total amount of unchanged amount of drug removed by hemodialysis (A_{rem}) from time 0 to 1 hour after the start of hemodialysis ($A_{rem}(0-1)$), A_{rem} from time 1 to 2 hours after the start of hemodialysis ($A_{rem}(1-2)$), A_{rem} from time 2 to 3 hours after the start of hemodialysis ($A_{rem}(2-3)$), A_{rem} from time 3 to 4 hours after the start of hemodialysis ($A_{rem}(3-4)$), cumulative amount of drug removed by hemodialysis from time 0 to 4 hours (or to the end of dialysis if less than 4 hours; $A_{rem}(0-4)$), partial area under the curve estimated from predialyzer samples collected from start of dialysis (t₀) to end of dialysis (t₁; $AUC(t_0-t_1)$), dialysis clearance (CL_D), and fraction (%) of the dose removed by hemodialysis from 0 to 4 hours after the start of hemodialysis (or to the end of dialysis if less than 4 hours; $F_{rem}\%(0-4)$). Dialysate concentrations (Group F) of gepotidacin and the associated PK parameters will be listed, and summary statistics (n, mean, median, standard deviation, minimum, maximum, and coefficient of variation) will be presented by day and treatment.

Safety endpoints will include monitoring adverse events, clinical laboratory results, vital sign measurements 12-lead electrocardiogram measurements, and physical examination findings.

2. INTRODUCTION

Gepotidacin is a novel triazaacenaphthylene bacterial topoisomerase inhibitor, which inhibits bacterial DNA replication and has *in vitro* activity against susceptible and drug-resistant pathogens associated with a range of conventional and biothreat infections.

Gepotidacin has demonstrated *in vitro* activity and *in vivo* efficacy against conventional and biothreat pathogens, including isolates resistant to existing classes of antimicrobials. Gepotidacin selectively inhibits bacterial DNA gyrase and topoisomerase IV by a unique mechanism, which is not utilized by any currently approved human therapeutic agent. Structural data with a type II topoisomerase, DNA gyrase, reveals the novel binding mode of the class and distinguishes it from the binding mode of the quinolone antibacterials [Bax, 2010]. As a consequence of its novel mode of action, gepotidacin is active *in vitro* against target pathogens carrying resistance determinants to established antibacterials, including fluoroquinolones.

2.1. Study Rationale

In a previous absorption, distribution, metabolism, and excretion study for gepotidacin (See GSK Document Number 2014N189951_00 Study ID Study BTZ115774), the mean recovery of radioactivity in urine accounted for approximately 60% of [¹⁴C]-gepotidacin administered as a single IV dose. In addition, renal clearance of gepotidacin has been estimated to be approximately 40% of total systemic drug clearance. Therefore, renal impairment has the potential to adversely affect the elimination of gepotidacin.

It is expected that potential patients in future gepotidacin Phase III studies may have at least some degree of renal impairment. The results from this study will enable the development of appropriate dosing recommendations in patients with impaired renal function.

2.2. Brief Background

Gepotidacin has demonstrated clinical efficacy in a Phase II study for acute bacterial skin and skin structure infections, and is currently being evaluated in a Phase II study for gonorrhea.

3. OBJECTIVES AND ENDPOINTS

Objectives	Endpoints
Primary	

 To compare the pharmacokinetics of gepotidacin administered as a 750-mg IV dose in normal healthy subjects compared with subjects with mild, moderate, and severe renal impairment, and with subjects with end-stage renal disease (ESRD) 	
 Plasma primary pharmacokinetic (PK) endpoints include AUC(0-∞) and Cmax of gepotidacin, as data permit Urine primary PK end points include Ae total, fe%, and CLr of gepotidacin, as data permit Dialysate primary PK end points include AUC(t0-t1), CLD, and Frem%(0-4), of gepotidacin, as data permit
Secondary	

 To assess the safety and tolerability of gepotidacin administered as a 750-mg IV dose in normal healthy subjects compared with subjects with mild, moderate, severe renal impairment, and with subjects with ESRD 	
 12-lead safety electrocardiogram readings, change from baseline in vital sign measurements (blood pressure and heart rate), monitoring of adverse events, toxicity grading of clinical laboratory test results, and physical examinations

 To evaluate the secondary PK parameters of gepotidacin administered as a 750-mg IV dose in normal healthy subjects compared with subjects with mild, moderate, and severe renal impairment, and with subjects with ESRD 	
 Plasma PK endpoints include AUC(0-t), CL, λz, t1/2, Tmax, Vss, and Vz, as data permit Urine PK endpoint includes Ae(t1-t2), as data permit Dialysate PK endpoints include Arem(0-1), Arem(1-2), Arem(2-3), Arem(3-4), and Arem(0-4), as data permit
Exploratory	

 To evaluate the saliva pharmacokinetics of gepotidacin (subjects in Part 1 only) 	
 Primary PK endpoints include AUC(0-∞) and Cmax of gepotidacin, as data permit Secondary PK endpoints include AUC(0-t), CL, λz, t1/2, Tmax, Vss, and Vz, as data permit

ESRD = end-stage renal disease; PK = pharmacokinetic

4. STUDY DESIGN

4.1. Overall Design

This is a Phase I, nonrandomized, open-label, parallel-group, multi-center, multi-part study that will evaluate the pharmacokinetics, safety, and tolerability of a single IV dose of gepotidacin 750 mg over 2 hours in subjects with normal renal function; subjects with mild, moderate, and severe renal impairment; and subjects with end-stage renal disease (ESRD; on dialysis and not on dialysis). Subjects with renal impairment will be matched to subjects with normal renal function in terms of gender distribution, age (approximately ±10 years), and body mass index (BMI; approximately ±20%).

At Screening, subjects will be enrolled to the appropriate groups based on the classification as defined in the Food and Drug Administration (FDA) draft guidance for

[figure not shown]
industry, “Pharmacokinetics in Patients with Impaired Renal Function – Study Design, Data Analysis, and Impact on Dosing and Labeling” [DHHS, 2010]. Subjects with normal renal function and subjects with renal impairment will be classified based on the estimated glomerular filtration rate (eGFR; based on the Modification of Diet in Renal Disease Study). Subjects with normal renal function will also be classified based on estimated creatinine clearance (Clcr). For more details see Section 6.2.

This will be a multi-part study, in which pharmacokinetic (PK) requirements must be met (observed mean values: area under the curve [AUC] <48 $\mu\text{g}\cdot\text{hr}/\text{mL}$ and maximum observed concentration [Cmax] <14 $\mu\text{g}/\text{mL}$); and safety and tolerability will be reviewed before enrolling subjects into the next part of the study. In Part 1, subjects with normal renal function; subjects with moderate renal impairment; and subjects with severe renal impairment and subjects with ESRD not on hemodialysis will be enrolled. In Part 2 (optional), subjects with normal renal function, subjects with mild renal impairment, and subjects with ESRD on hemodialysis will be enrolled based on the PK, safety, and tolerability data of Part 1. Subjects with mild renal impairment may be studied if there is a significant difference in PK between subjects with moderate and severe renal impairment compared to subjects with normal renal function and modelling cannot accurately predict PK in subjects with mild renal impairment. Subjects with ESRD on hemodialysis will be studied provided that the PK requirements are met (observed mean values in subjects with severe impairment do not exceed the threshold: area under the curve [AUC] <48 $\mu\text{g}\cdot\text{hr}/\text{mL}$ and maximum observed concentration [Cmax] <14 $\mu\text{g}/\text{mL}$). The dose may be adjusted for subjects with ESRD on hemodialysis if either PK parameter is predicted to exceed the threshold. See the study schematic in Figure 1 for more details.

For subjects with normal renal function, subjects with mild, moderate, and severe renal impairment, and subjects with ESRD not on dialysis: subjects will participate in 1 treatment period and blood and urine samples will be collected for PK analysis of gepotidacin concentrations according to the Time and Events Tables (Table 2 and Table 3). In addition, saliva samples (subjects in Part 1 only) will be collected for the PK analysis of gepotidacin concentrations according to the Time and Events Tables (Table 2 and Table 3). Blood, urine, and saliva samples will be collected up to approximately 48 hours after dosing.

For subjects with ESRD on hemodialysis: subjects will participate in 2 treatment periods and blood and urine (if applicable) samples in Period 1 will be collected for PK analysis of gepotidacin concentrations according to the Time and Events Tables (Table 4 and Table 5). Blood and urine (if applicable) samples will be collected up to approximately 48 hours after dosing (i.e., the last sample will be collected before the next hemodialysis session). In addition, dialysate samples will be collected for the determination of gepotidacin concentrations according to the Time and Events Tables (Table 4 and Table 5).

Optional PK Assessment: with the subject’s consent, if a kidney or bladder tissue sample is collected for a nonstudy purpose during this study, excess tissue may be collected and used for the purposes of measuring tissue gepotidacin concentrations.

Figure 1 BTZ116849 Study Schematic

ESRD = end-stage renal disease; PK = pharmacokinetic

- ^a If there are a sufficient number of subjects with normal renal function enrolled in Part 1 (Group A), a determination will be made regarding enrollment of matching subjects with normal renal function in Part 2 (Group D).
- ^b Based on emerging data from Part 1, Group E (subjects with mild renal impairment) may not be enrolled in Part 2 if there is not a significant difference between subjects with moderate and severe impairment compared to subjects with normal renal function or if the PK can be accurately predicted.
- ^c If AUC and/or Cmax is predicted to exceed the threshold, the dose may be adjusted in Group F (optional).

In Part 2 (optional) of the study, subjects in Group F will participate in 2 treatment periods, with dosing in these periods separated by a washout period of at least 7 days. Subjects in Group F will enter the clinic at Check-in (Day -1, Period 1 and Day 7, Period 2) before each study drug administration (Day 1, Period 1 and Day 8, Period 2). On Day 1 (Period 1) and Day 8 (Period 2), subjects in Group F will receive a single dose of study drug as follows: gepotidacin 750 mg administered as a 2-hour IV infusion starting approximately 2 hours before the initiation of the last hemodialysis session of the week (Period 1) and gepotidacin 750 mg administered as a 2-hour IV infusion starting within 2 hours after completion of the last hemodialysis session of the week (Period 2). Subjects in Group F will be discharged from the clinic on Day 10 of Period 2 after all scheduled PK and safety assessments have been completed, and will return to the clinic for a Follow-up Visit approximately 10 days (± 5 days) after the last dose administration in Period 2. The duration of the study (from Screening to the Follow-up Visit) will be approximately 50 days.

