7. STUDY ASSESSMENTS AND PROCEDURES

Protocol waivers or exemptions are not allowed with the exception of immediate safety concerns. Therefore, adherence to the study design requirements, including those specified in the Time and Events Tables are essential and required for study conduct.

This section lists the procedures and parameters of each planned study assessment. The exact timing of each assessment is listed in the Time and Events Tables, Section 7.1.

The following points must be noted:

- If assessments are scheduled for the same nominal time, THEN the assessments should occur in the following order:
 1. 12-lead ECG
 2. vital signs
 3. blood draws

Note: The timing of the assessments should allow the blood draw to occur at the exact nominal time.

- The timing and number of planned study assessments, including safety and PK assessments, may be altered during the course of the study based on newly available

data (e.g., to obtain data closer to the time of peak plasma concentrations) to ensure appropriate monitoring.

- The change in timing or addition of time points for any planned study assessments must be documented in a Note to File which will be approved by the relevant GSK study team member and then archived in the study sponsor and clinic study files, but this will not constitute a protocol amendment.
- The institutional review board (IRB)/independent ethics committee (IEC) will be informed of any safety issues that require alteration of the safety monitoring scheme or amendment of the informed consent form (ICF).
- No more than 500 mL of blood will be collected over the duration of the study, including any extra assessments that may be required.

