Blood collection for pharmacokinetics			X	X	X			X	X	X			See Table 5 for time points.
Urine collection for pharmacokinetics			X	X	X			X	X	X			See Table 5 for time points. Subjects may not be able to produce a urine sample.
Dialysate collections for pharmacokinetics			X	X	X								See Table 5 for time points.
AE/SAE review	X	X	←=====→								X		
Concomitant medication review		X	←=====→					←=====→			X		

Footnotes continued on the next page.

AE = adverse event, eGFR = estimated glomerular filtration rate, ECG = electrocardiogram, FSH = follicle-stimulating hormone; HIV = human immunodeficiency virus, PGx = pharmacogenetic, SAE = serious AE; WCBP = women of childbearing potential.

- a For subjects on hemodialysis (Part 2 [optional], Group F), assessments performed on scheduled hemodialysis days are to be done before hemodialysis (except for PK sample collection, which will be done before and after hemodialysis).
- b Subjects in Group F will participate in 2 treatment periods, with dosing in these periods separated by a washout period of at least 7 days. Subjects in Group F will enter the clinic at Check-in (Day -1, Period 1 and Day 7, Period 2) before each study drug administration (Day 1, Period 1 and Day 8, Period 2). On Day 1 (Period 1) and Day 8 (Period 2), subjects in Group F will receive a single dose of study drug as follows: gepotidacin 750 mg administered as a 2-hour IV infusion starting approximately 2 hours before initiation of the last hemodialysis session of the week (Period 1) and gepotidacin 750 mg administered as a 2-hour IV infusion starting within 2 hours after completion of the last hemodialysis session of the week (Period 2). Subjects in Group F will be discharged from the clinic on Day 10, Period 2.
- c If test has otherwise been performed within 3 months prior to first dose of study treatment, testing at Screening is not required.
- d Informed consent for optional substudies (e.g., genetics research) must be obtained before collecting a sample.

Table 5 Safety and Pharmacokinetic Assessments (Group F)

Procedure ^a	Predose	Treatment Periods 1 and 2															
		Time point (hours) ^a															
		0	0.25	0.5	1	1.5	2	2.5	3	4	6	8	12	24 ^b	36 ^b	48 ^b	
12-lead electrocardiogram	X						X ^c			X		X	X	X	X	X	
Vital signs	X						X ^c			X		X	X	X	X	X	
Treatment administration 2-hour IV gepotidacin infusion ^d		X															
Blood collection for pharmacokinetics	X		X	X	X	X	X	X	X	X	X	X	X	X	X	X	

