Urine collection for pharmacokinetics ^e	X	X										X	X	X	X	X	
Dialysate collection for pharmacokinetics ^f	X	X		X		X		X									

^a When coinciding with safety and/or pharmacokinetic assessments, electrocardiograms, vital signs, and pharmacokinetic blood collections should be performed in said order.

^b The 24-, 36-, and 48-hour postdose time points correspond to time points on Day 2 and 3, respectively.

^c Performed post infusion.

^d Subjects in Group F will participate in 2 treatment periods, with dosing in these periods separated by a washout period of at least 7 days. Subjects in Group F will enter the clinic at Check-in (Day -1, Period 1 and Day 7, Period 2) before each study drug administration (Day 1, Period 1 and Day 8, Period 2). On Day 1 (Period 1) and Day 8 (Period 2), subjects in Group F will receive a single dose of study drug as follows: gepotidacin 750 mg administered as a 2-hour IV infusion starting approximately 2 hours before initiation of the last hemodialysis session of the week (Period 1) and gepotidacin 750 mg administered as a 2-hour IV infusion starting within 2 hours after completion of the last hemodialysis session of the week (Period 2). Subjects in Group F will be discharged from the clinic on Day 10, Period 2.

^e It should be noted that subjects in Group F may not be able to produce urine samples due to their medical condition. All sampling times are relative to the start of the infusion.

^f Dialysate fluid will be collected on Day 1 after dosing (Period 1 only) over each 1-hour collection interval of the hemodialysis session.

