**Table 4 Derived Plasma Pharmacokinetic Parameters**

Parameter	Parameter Description
AUC(0-t)	Area under the concentration-time curve from time 0 (predose) to time of last quantifiable concentration, to be calculated using the linear trapezoidal rule for each incremental trapezoid and the log trapezoidal rule for each decremental trapezoid.
AUC(0-∞)	Area under the concentration-time curve from time 0 (predose) extrapolated to infinite time, calculated as: $AUC = AUC(0-t) + C(t) / \lambda z$
%AUCex	The percentage of AUC (0-∞) obtained by extrapolation (%AUCex) will be calculated as: $[AUC(0-inf) - AUC(0-t)] / AUC(0-inf) \times 100$
Cmax	Maximum observed concentration, determined directly from the concentration-time data.
Tmax	Time to first occurrence of Cmax
t 1/2	Terminal half-life will be calculated as: $t_{1/2} = \ln 2 / \lambda z$
λz	Terminal-phase rate constant
CL	Systemic clearance, calculated as: $CL = Dose / AUC(0-\infty)$
V ss	Volume of distribution at steady-state of parent drug, calculated as: $V_{ss} = MRT(0-inf) * CL$
V z	Volume of distribution of the terminal phase, calculated as: $V_z = Dose / (\lambda z * AUC(0-inf))$

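### At the Group F 2-hour time point, the post-infusion ECG and vital signs, the assessment order and the fixed blood-draw time cannot all be followed, so Cmax may be sampled late

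*Protocol*

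**What the plan says.** - **Dosing, Protocol Section 4.2.** In Period 1, Group F receives a "2-hour IV infusion starting approximately 2 hours before the initiation of the last hemodialysis session of the week (Period 1"). In Period 2 it receives a "2-hour IV infusion starting within 2 hours after completion of the last hemodialysis session of the week (Period 2"). The nominal end of infusion is 2 h in both periods. Only in Period 1 does dialysis start at about that time.
- **Group F schedule, Protocol Table 5 (both periods; repeated in SAP Appendix 1).** ECG, vital signs and PK blood all fall at 2 h. Footnote c to the ECG and vital signs reads "Performed post infusion". Footnote a reads "When coinciding with safety and/or pharmacokinetic assessments, electrocardiograms, vital signs, and pharmacokinetic blood collections should be performed in said order".
- **Groups A to E, Protocol Table 3.** The same three assessments fall at 2 h under the same order, but there is no post-infusion footnote.
- **All groups, Protocol Section 7.** The order is stated again, with the note "The timing of the assessments should allow the blood draw to occur at the exact nominal time".
- **Dialysis days, Protocol Table 4, footnote a.** In Group F, "assessments performed on scheduled hemodialysis days are to be done before hemodialysis (except for PK sample collection").
- **Analysis.** SAP Table 4 defines Cmax as "Maximum observed concentration, determined directly from the concentration-time data". SAP Section 7.1.3.1 bases noncompartmental calculations on actual sampling times.

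**The concern.** During a constant infusion the concentration rises until the infusion stops and then falls, so for a 2-hour infusion the 2-hour sample is the one that should capture the peak. If the ECG and vital signs wait for the infusion to stop, and the blood waits for the ECG and vital signs, that sample is taken on the falling part of the curve. Cmax is the highest observed value, so recording the actual time puts the AUC calculation right but cannot recover a peak that was missed.

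Cmax is a primary endpoint. The Group F comparison with normal renal function could then set a post-infusion value against an end-of-infusion value. The protocol also links cholinergic effects to Cmax (Section 4.6.1), and Section 6.3 lets Group F Period 1 data inform the Period 2 dose. Sites that resolve the conflict differently would add a site difference to a group of about 4 to 8 subjects.

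**Working it through.** **1. Can the instructions be met together?** Take the infusion as running from 0 to 2 h.

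- Footnote c: ECG and vital signs after 2 h.
- Footnote a: blood after the ECG and vital signs, hence also after 2 h.
- Section 7: blood at 2 h exactly.

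The first two together exclude the third. In Groups A to E footnote c is absent, so ECG and vital signs can be done in the last minutes of the infusion and blood drawn at 2 h, which meets every rule.

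Period 1 adds a further tension. Under Table 4, footnote a, the ECG and vital signs must come before hemodialysis. Footnote c puts them after the infusion. The infusion stop and the dialysis start are nominally about the same moment.

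**2. Size if the draw is late.** The documents give no delay, so 5, 10 and 15 minutes are assumptions. Table 1 values for severe impairment stand in for Group F, also an assumption: AUC 28.9 µg·h/mL, Cmax 7.93 µg/mL, dose 750 mg, infusion rate 375 mg/h.

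- CL = 750/28.9 = 25.95 L/h.
- One compartment: (375/25.95) × (1 − exp(−2k)) = 7.93 gives k = 0.398/h and V = 25.95/0.398 ≈ 65 L.
- Loss after m minutes = 1 − exp(−0.398 × m/60): 3.3%, 6.4% and 9.5% at 5, 10 and 15 minutes.

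Wider assumptions: V from 60 to 91 L (91 = 1.30 × 70, reading the Appendix 11 volume as L/kg at an assumed 70 kg) and dialysis clearance from 0 to 12 L/h (assumed). With loss = 1 − exp(−((25.95 + CLD)/V) × m/60):

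| Delay | V = 91 L, CLD = 0 | V = 60 L, CLD = 0 | V = 60 L, CLD = 12 L/h |
|---|---|---|---|
| 5 min | 2.3% | 3.5% | 5.1% |
| 10 min | 4.6% | 7.0% | 10.0% |
| 15 min | 6.9% | 10.2% | 14.6% |

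The last column could apply only in Period 1, and only if dialysis were already running.

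**3. Upper limit.** The 1.5-hour sample also counts towards Cmax. In the base model C(1.5)/C(2) = (1 − exp(−0.398 × 1.5))/(1 − exp(−0.398 × 2)) = 0.82. Over V = 60 to 91 L the ratio is 0.82 to 0.80. The fall in Cmax is therefore capped at about 18-20%.

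**4. Effect on a ratio, for scale.** Table 1 implies a severe-to-normal Cmax ratio of 7.93/5.65 = 1.40. If only the impaired group were sampled late, it would read 1.40 × 0.967 = 1.36 at 5 minutes and 1.40 × 0.905 = 1.27 at 15 minutes.

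**5. Against the planned precision.** Protocol Section 9.2.1 states a 90% CI half width of 21.77% for Cmax with 16 versus 8 subjects and CV 26.3%. Using exp(t(0.95, 22 df) × SD × √(1/16 + 1/8)) − 1, I get 21.2% with SD = √ln(1 + CV²) and 21.6% with the CV used as SD, so the figure is reproduced closely. The losses in step 2 are all smaller than this half width.

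**The case against.** A reader might infer that Group F Cmax will be sampled late and will understate exposure against normal subjects. The documents do not establish that, for several reasons.

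- **Section 7 can be read as the governing rule.** Its note sits directly under the assessment order and says how to apply it: the draw time is fixed and the other assessments move. A site that reads it so draws at 2 h and loses nothing. This stands. It makes lateness conditional but does not remove the conflict, because Table 5 is the more specific instruction for this group and a site could reasonably follow it.
- **The order itself is shared.** If it delayed the draw equally in normal subjects, they would lose at least as much, because they clear the drug faster (750/17.5 = 42.9 L/h): 3.8-5.8% at 5 minutes against 2.3-5.1% in Group F over the same V range. Group F would then not read low. Nothing in Table 3 forces such a delay, however; only footnote c does, and it applies to Group F alone.
- **The delay may be short.** ECGs are single (Section 7.3.5), and the 5-minute rest before vital signs (Section 7.3.4) could be completed during the infusion. At k = 0.398/h, 2 to 3 minutes costs 1.3-2.0%. This is fair.
- **Dialysis need not have started.** Section 4.2 says only approximately 2 hours, Table 4 puts the ECG and vital signs before hemodialysis, and Period 2 dosing follows dialysis. So the documents do not show drug being dialysed out before the sample.
- **The exposure threshold is not at stake for entry.** Whether Group F is studied depends on Part 1 means in severe impairment (Section 4.1). Only the Period 2 dose could draw on Group F Period 1 data.
- **The SAP already lists planned and actual times** and provides for assessing major timing deviations (Section 9.3.3). That makes a late draw visible but does not prevent it.

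**Conclusion.** The conflict is real and specific to Group F, in both periods: three instructions at the 2-hour time point cannot all be met. If a site follows the Table 5 order, the end-of-infusion sample is late and Cmax may read modestly low. The size is about 3% at 5 minutes and 10% at 15 minutes in the one-compartment model, and 2-5% and 7-15% under the wider assumptions, with a ceiling of about 18-20% set by the 1.5-hour sample. A fast distribution phase would make the loss larger for a given delay, still limited by that sample.

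These sizes rest on an assumed delay, simulated severe-impairment values standing in for dialysis subjects, and, at the upper end, an assumed dialysis clearance. They are small against the planned 21.77% half width, although enrolling more subjects would not remove a loss of this kind. The documents support a contradiction that puts Cmax at risk. They do not support an established or necessarily one-directional bias. It is worth correcting because it touches a primary endpoint and costs almost nothing to resolve.

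**What to change.** - In Protocol Table 5 and the matching table in SAP Appendix 1, exempt the Group F 2-hour PK draw from the order ECG, vital signs, blood. Define it at the same point relative to the end of infusion as in Groups A to E, with the post-infusion ECG and vital signs after it.
- Reconcile Section 4.2 (Period 1 timing), Table 4 footnote a and Table 5 footnote c, so that a site can tell how the 2-hour assessments sit relative to the end of infusion and the start of hemodialysis.
- In the SAP plasma concentration listing, flag any 2-hour sample whose actual time is later than the recorded infusion stop. All profiles stay in the analysis.

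The cost is one table footnote made consistent in two documents, a cross-check of the dialysis-day wording, and one listing flag. It needs no extra samples, visits or subjects.
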